6.3.2.3. Analysis of HCV RNA (log₁₀ IU/mL)

Summary statistics will be presented for absolute values and change from baseline in HCV RNA (log10 IU/mL) at each visit through EOT. Imputation rules described in Section 3.6.1 will be used to assign HCV RNA values for missing values at a visit that are bracketed by "< LLOQ TND" and/or "< LLOQ detected". Otherwise, a missing = excluded analysis will be performed.

6.3.2.4. Analysis of HCV Virologic Failure at Post HCV Treatment Weeks 4 and 12

For the SVR4 endpoint analysis, a summary table of the number and percentage of subjects with SVR4, virologic failure (VF), and Other will be created. This summary will be performed for each HCV genotype (1a, 1b, and other if applicable) and overall broken down by treatment group and total. All subjects who achieve SVR4 will be categorized as SVR4. Virologic failure will be descriptively summarized as "on-HCV-treatment virologic failure" and relapse (which will be broken down by study drug completed yes/no). Subjects who do not achieve SVR4 and do not meet criteria for virologic failure will be categorized as Other. The denominator for relapse will be the number of subjects who had HCV RNA < LLOQ on their last observed on-HCV-treatment HCV RNA measurement; otherwise, the denominator will be the number of subjects in the HCV FAS.

The same analysis method will be applied to SVR12 endpoint analysis.

In addition, a summary table of the number and percentage of subjects with HCV RNA < LLOQ and ≥ LLOQ at the posttreatment follow-up visit (observed and imputed, with reasons for imputed) for each treatment group will be provided for each posttreatment follow-up visit by HCV genotype and overall. The 2-sided 95% Clopper-Pearson exact CIs will be presented for the overall proportion of subjects with HCV RNA < LLOQ.

6.3.2.5. Analysis of the Proportion of Subjects with HIV-1 RNA ≥ 20 copies/mL as Determined by US FDA-defined Snapshot algorithm

The proportion of Subjects with HIV-1 RNA \geq 20 copies/mL as determined by US FDA-defined Snapshot algorithm 24 weeks after start of the HIV study drug will be analyzed using exactly the same method used for the secondary HIV efficacy endpoint with cutoff 50 copies/mL, as specified in Section 6.2.2.2, excluding the subgroup analysis.

6.3.2.6. Analysis of the Proportion of Subjects with HIV-1 RNA < 50 copies/mL (Missing = Excluded and Missing = Failure Approaches)

The proportion of subjects with HIV-1 RNA < 50 copies/mL will also be analyzed using the M = F and M = E for imputing missing HIV-1 RNA values, where the proportions will be expressed as percentages in all tables, listings, and figures.

For both M = F and M = E analyses, the number and percentage of subjects with HIV-1 RNA in the following categories will be summarized:

- < 50 copies/mL
- < 20 copies/mL
 - < 20 Not Detectable
 - < 20 Detectable
- 20 to < 50 copies/mL
 - $-- \ge 50 \text{ copies/mL}$
 - Missing (only applicable for M = F analysis)

The proportion of subjects with HIV-1 RNA < 50 copies/mL as defined by the 2 different missing data imputation methods will be summarized by treatment group and overall. The differences in proportions of subjects with HIV-1 RNA < 50 copies/mL using M = E and M = F imputation methods between the 2 treatment groups and the corresponding two-sided exact 95% CIs will be calculated based on an unconditional exact methods using 2 inverted 1-sided tests. In addition, the 95% CI of the proportion of subjects with HIV-1 RNA < 50 copies/mL within each treatment at each visit will be provided using the Clopper-Pearson Exact method.

For both M = F and M = E analysis, results will be summarized by treatment group for all visits.

6.3.2.7. Analysis of CD4+ Cell Count and CD4 %

Both CD4 cell count and CD4 % will be summarized using observed, on-HIV-treatment data (ie, data collected up to 1 day after permanent discontinuation of HIV study drug or all available data for subjects who are still on HIV study drug) for subjects in the HIV FAS.

The change from baseline in CD4+ cell count will be summarized by visit for each treatment group and over all using descriptive statistics. The differences in changes from baseline 24 weeks after start of HIV study drug in CD4+ cell count between the 2 treatment groups and the associated 95% CI will be constructed using ANOVA models, including treatment group and race as fixed effects.

In addition, the change from baseline in CD4+ cell counts with missing values imputed using the last observation carried forward (LOCF) method will be summarized at each visit based on the FAS. The algorithm for LOCF as follows:

- If a value is missing in an analysis visit window, the missing value will be replaced with the last on-HIV-treatment value (ie, data collected up to 1 day after the last dose date of HIV study drug) observed before the analysis visit window that has the missing value.
- Baseline values will be carried forward to impute the postbaseline value at a specific visit, if there is no nonmissing postbaseline observation collected prior to that visit.

CD4% will be analyzed the same as CD4+ cell count, except that the by-visit summary using LOCF method is not planned for CD4%.

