1.2.2. Randomization and Treatment Groups

Part 1: Approximately 120 subjects will be randomized 1:1 to switch from stable ARV therapy to 1 of the following treatments:

- **Treatment Group 1:** Switch from 2 nucleoside/nucleotide reverse transcriptase inhibitor (NRTI) plus a third ARV agent to E/C/F/TAF fixed dose combination (FDC) (n = 60)
- Treatment Group 2: Switch from 2 NRTI plus a third ARV agent to F/R/TAF FDC (n = 60)

Randomization will be stratified by race (black vs non-black).

Part 2: After 8 weeks on the randomized F/TAF-based regimens, subjects maintaining HIV-1 RNA < 50 copies/mL and tolerating E/C/F/TAF or F/R/TAF through Part 1 will continue the F/TAF-based HIV therapy to which they were randomized and initiate LDV/SOF HCV treatment.

• LDV/SOF FDC tablet once daily for 12 weeks.

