3.3. Strata and Covariates

Randomization was stratified by race (black or non-black) to provide balance across treatment groups.

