Last Study Date is the latest of nonmissing study drug start dates and end dates, the clinic visit dates, and the laboratory visit dates including the 30-day follow-up visit date for subjects who prematurely discontinued study or who completed study according to Study Completion eCRF.

Study Baseline Value is defined as the last value obtained on or prior to Study Day 1 for all assessments.

Part 2 Baseline value is defined as the last value obtained on or prior to LDV/SOF Day 1 for all safety assessments in Part 2 and HCV RNA in Part 2.

In general, the baseline value will be the last nonmissing value on or prior to the first dose date of study drug.

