b) Fisher's exact test for categorical efficacy response (eg, HIV-1 RNA < 50 copies/mL in US FDA-defined snapshot algorithm), where *trtgrp* is the treatment, and *response* is the categorical efficacy response. P-value from 2-sided Fisher's exact test should be used to test superiority.

```
proc freq data=adeff;
   tables trtgrp*response/fisher; /*p value from Fisher's exact test*/
run:
```

c) ANOVA model for continuous efficacy variable (eg, CD4):

The differences in changes from baseline in CD4 cell count between treatment groups and the associated 95% CI will be constructed using ANOVA, including the prior treatment regimen as fixed effects in the model.

SAS code is as follows:

```
proc glm data=adeffi;
  class trtgrp;
  model CD4 = trtgrp;
  lsmeans trtgrp /alpha=0.05 cl pdiff;
run;
```

Similar code will be used for the analysis of CD4 %.

d) Subgroup analyses

For the subgroups of age, race, sex, region and study drug adherence, p-value from 2-sided Exact method should be used to test superiority. The proportion difference between two treatment groups and 95% CIs are calculated based on an unconditional exact method using 2 inverted 1-sided tests, similarly to that for the primary efficacy endpoint.

14) Treatment-emergent AE (TEAE)

Events with Missing Onset Day and/or Month

The event is treatment emergent in a safety period, if the following 3 criteria are met:

- a) The month and year (or year) of onset date is the same as or after the month and year (or year) of the start date of the safety period, and
- b) The month and year (or year) of the onset date is the same as or before the month and year (or year) of safety cutoff date of the safety period, and
- c) AE end date is as follows:
 - i) The (complete) AE end date is on or after the safety period start date, or
 - ii) The month and year (or year) of end date is the same or after the month and year (or year) of the safety period start date, or
 - iii) AE end date is completely missing.

Events with Completely Missing Onset Date

An AE with a completely missing onset date is defined as TEAE for a safety period if AE end date meets any of the criteria specified in 3) above.

15) Renal related laboratory evaluation

Urine Protein Correction

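### The between-arm Week 24 CD4 model leaves out the baseline value and is stated in three different ways; a tertiary estimate loses some precision

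*SAP*

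**What the plan says.** SAP 6.3.2.7, under the tertiary efficacy endpoints, defines the contrast as "The differences in changes from baseline 24 weeks after start of HIV study drug in CD4+ cell count between the 2 treatment groups". It says that the difference and its 95% CI "will be constructed using ANOVA models, including treatment group and race as fixed effects". The data are observed, on-HIV-treatment values in the HIV FAS. CD4% gets the same analysis, apart from the LOCF summary.

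SAP Appendix 4, item 13c restates this model twice, differently each time:

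- Its text says that the interval is "constructed using ANOVA, including the prior treatment regimen as fixed effects in the model". Race is not named.
- Its code reads "model CD4 = trtgrp". There is no race term and no prior-regimen term, and the response is labelled CD4 rather than change in CD4.

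The baseline value is in none of the three. It is available: the study procedures table schedules CD4+ count at Screening and Day 1, and SAP 3.8.1 states that "Study Baseline Value is defined as the last value obtained on or prior to Study Day 1 for all assessments".

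On balance, SAP 3.3 says "Randomization was stratified by race (black or non-black) to provide balance across treatment groups". Race is the only stratification factor, so nothing in the design balances baseline CD4. On size, SAP 1.2.2 says "Approximately 120 subjects will be randomized 1:1", or 60 per arm.

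**The concern.** Change from baseline is usually negatively correlated with baseline, because subjects who start high tend to fall back and those who start low tend to rise. If the arms differ in baseline CD4 by chance, a change-score model without the baseline value turns part of that difference into an apparent treatment difference. It also leaves in the residual the variation that baseline would have explained, so the CI is wider than necessary.

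The eligibility criteria (Protocol 4.2 and 4.3) set no CD4 limits, and the SAP 5.2 baseline categories run from below 50 to 500 or more, so the baseline spread may be wide. SAP 5.2 also plans a Wilcoxon comparison of the arms on continuous baseline characteristics, including CD4 count. The plan therefore looks for an imbalance but has no stated way to handle one.

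At stake are the width and the conditional accuracy of one reported between-arm estimate for CD4+ count and one for CD4%. There is also a practical risk: a programmer following Appendix 4 would fit a different model from the one in the SAP body.

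**Working it through.** **No planned figure to reproduce.** The documents state no SD, correlation, effect size, power or CI width for CD4.

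**Inputs.** n = 60 per arm (SAP 1.2.2). The SD (sigma) of CD4 and the baseline-to-Week-24 correlation (rho) are assumptions. Sigma is taken as equal at both times, and rho is shown over 0.5 to 0.9.

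**Formulas.** Variance of the difference between arms:

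- change-score ANOVA: 2(1 − rho) × sigma² × (2/n)
- ANCOVA: (1 − rho²) × sigma² × (2/n)
- ratio: (1 − rho²) / [2(1 − rho)] = (1 + rho)/2

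The CI width ratio is the square root of (1 + rho)/2. The total sample giving the planned precision under ANCOVA is 120 × (1 + rho)/2. Given a baseline difference D between arms, the unadjusted estimate shifts by −(1 − rho) × D; the adjusted estimate does not shift.

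| Assumed rho | Variance ratio | CI narrower by | Equivalent total n | Share of D carried over |
|---|---|---|---|---|
| 0.5 | 0.75 | 13.4% | 90 | −0.5 |
| 0.7 | 0.85 | 7.8% | 102 | −0.3 |
| 0.8 | 0.90 | 5.1% | 108 | −0.2 |
| 0.9 | 0.95 | 2.5% | 114 | −0.1 |

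**Simulation check.** With 60 per arm, a race term in both models and 4,000 replicates per rho, the variance ratios were 0.76, 0.86, 0.91 and 0.97. The slopes of the unadjusted estimate on D were −0.50, −0.30, −0.19 and −0.10. With ANCOVA the slope was at most 0.01 in absolute value. Under no effect, both estimators averaged about zero.

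**In cells/µL, with sigma assumed to be 250.**

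- SE of the chance baseline difference: 250 × √(2/60) = 45.6.
- rho 0.7: the shift for a one-SE imbalance is 0.3 × 45.6 = 13.7. The SE of the unadjusted difference is 250 × √0.6 × √(2/60) = 35.4, so the 95% half-width is 1.96 × 35.4 = 69. With adjustment the SE is 250 × √0.51 × √(2/60) = 32.6 and the half-width 64.
- rho 0.5: shift 22.8, unadjusted half-width 89.
- rho 0.9: shift 4.6, unadjusted half-width 40.

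The shift as a share of the unadjusted half-width does not depend on sigma. It is √[(1 − rho)/2]/1.96, or 26%, 20%, 16% and 11% at rho 0.5, 0.7, 0.8 and 0.9.

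**The case against.** The strongest reply is that this is a matter of efficiency on a minor endpoint. Most of it stands.

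- **Validity.** A change-score ANOVA in a randomized comparison is unbiased over repeated randomizations and its CI already allows for chance baseline variation. Lost precision and conditional shift are two views of one effect and should not be counted as two harms. At rho 0.7 the 14-cell shift is about 0.4 SE.
- **Stakes.** CD4 is tertiary, with no hypothesis, margin or power statement. Protocol 8.4.2 plans only descriptive CD4 summaries, at Week 8 and Post-HCV Treatment Week 12.
- **Size.** Entry requires a stable regimen and HIV suppression for about six months, which makes a high rho plausible, though the documents do not establish it. At 0.8 to 0.9 the CI gain is only 5% to 2.5%.
- **Visibility.** Baseline CD4 is tabulated and tested by arm, so a reader could see an imbalance. That does not correct the estimate.

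None of this justifies omitting a covariate that is already collected, or leaving three different model statements in the SAP.

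A reader might infer three stronger things that the documents do not support:

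- **That the treatment difference is biased.** It is not, over repeated randomizations.
- **That the whole baseline difference passes into the estimate.** Only the fraction (1 − rho) does, with reversed sign.
- **That the raw Week 24 count will be modelled, because of the response label in the code.** The sentence introducing that code speaks of changes from baseline, as does 6.3.2.7. The label is loose, not evidence of a different outcome.

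**Conclusion.** The point holds at low severity. Every version of the Week 24 between-arm CD4 model omits the baseline value, and the versions disagree on the other terms. The planned analysis is valid but less precise than it could be: CIs about 13% to 2.5% wider than ANCOVA's relative to the planned width, over an assumed rho of 0.5 to 0.9. A one-SE chance imbalance would move the estimate by roughly a quarter to a tenth of the CI half-width.

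The direction is secure for any rho below 1 with equal SDs. The size is not, because both rho and the SD of 250 cells/µL are assumptions. Fewer than 60 per arm with Week 24 data would leave the ratios essentially unchanged. SVR12, SVR4, the HIV snapshot endpoint and the safety analyses are untouched.

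**What to change.** Specify one model, in the same words, in SAP 6.3.2.7 and Appendix 4, item 13c:

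- CD4+ count: Week 24 change from baseline = treatment group + race stratum (black or non-black) + baseline CD4+ count.
- CD4%: the same, with baseline CD4% as the covariate.

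Report the adjusted difference with its 95% CI. In item 13c, replace the prior-regimen wording, add the race and baseline terms to the code, and name the response as the change. With the baseline value in the model, the treatment estimate is the same whether the response is the change or the Week 24 value, so the label can no longer alter the result.

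The cost is one covariate and an edit to two sections, with no new data. The edit should be dated and made before the Week 24 CD4 data are compared by arm. The administrative analysis in SAP 2.1 covers efficacy data through Post-HCV Treatment Week 4, which usually coincides with Week 24, so the change should precede it if possible.

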7. SAFETY ANALYSES

[figure not shown]
7.1. General Consideration for Safety Analysis

In general, safety data will be summarized for the subjects in the safety analysis set. Safety data collected up to 30 days after permanent discontinuation of all study drugs (including HIV study drug and LDV/SOF) and available data for subject who are still on study drug will be summarized by treatment group and overall, unless specified otherwise. All safety data will be included in listings.

7.1.1. Administration Periods for Safety Analysis

In the 2-part coinfection study, subjects receive different treatments at different periods of the study (Figure 7-1). Four administration periods, Part 1, Part 2, Co-administration, and Whole Study, are defined accordingly in Table 7-1 with start, end, and safety cutoff dates provided.

Figure 7-1. Study Treatments Received in Different Periods of Study

- a In Part 1 of the study, subject receive HIV study drug only.
- b Part 2 is applicable only if subjects took at least one dose of LDV/SOF.
- c Subjects who entered Part 2 receive both LDV/SOF and HIV study drug for at most 12 weeks and this is defined as the co-administration period. The co-administration period is terminated by permanent discontinuation of LDV/SOF or HIV study drug, which ever happens earlier;
- d By the end of co-administration period, if subject permanently discontinued LDV/SOF while still receiving HIV drug, HIV study drug will continue to be administered until the end of Part 2 as planned in protocol. If subject prematurely discontinued HIV study drug while still receiving LDV/SOF, LDV/SOF will continue to be administered until 12 weeks of HCV treatment is completed. If subject permanently discontinued both LDV/SOF and HIV study drug at the same date, no study drug will be administered after the co-administration period until the end of Part 2.

	, ,	•				
Administration Period	Start Date	End Date	Safety Cutoff Date			
Part 1	HIV study drug first dose date	Minimum of HIV study drug last dose date and Part 2 Day 1	End date if subject is ever dosed with LDV/SOF; or end date + 30 days if subject is never dosed with LDV/SOF			
Part 2	HCV study drug first dose date if applicable	Maximum of HIV and HCV study drug last dose dates if applicable	30 days after Part 2 period end date			
Co-administration	HCV study drug first dose date if applicable	Minimum of HIV and HCV study drug last dose dates if applicable	30 days after Co-administration period end date			
Whole Study	HIV study drug first dose date	Maximum of HIV and HCV study drug last dose dates	30 days after Whole Study period end date			

Table 7-1. Start, End, and Safety Cutoff Dates of All Administration Periods

Summary of safety data is planned by administration periods as below:

- Adverse events and laboratory abnormalities will be summarized for Part 1, Co-administration, and Whole Study periods respectively.
- By-visit laboratory assessment and vital signs will be summarized for Whole Study and Part 2 periods respectively.
- Concommitant medication will be summarized for Whole Study period only.

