6.5. Post-treatment Assessments

6.5.1. Early Study Drug Discontinuation (ESDD) Visit

Early study drug discontinuation during Part 1 (Day 1 through Week 8):

If the subject discontinues HIV study drug dosing in Part 1, the subject will be discontinued from the study and will not continue to Part 2 of the study. The subject will be asked to return to the clinic within 72 hours of stopping HIV study drugs for the ESDD visit, followed by the 30-Day Follow-Up visit.

Early study drug discontinuation during Part 2 (after initiation of HCV treatment):

If the subject discontinues HCV study drug dosing only prior to completing the 12-week HCV treatment, the following will occur:

- Be asked to return to the clinic within 72 hours of stopping HCV study drug for the ESDD visit.
- Remain in the study to return for follow-up visits 4 and 12 weeks after the last dose of LDV/SOF, as described in Section 6.4.2.
- Continue to receive HIV study drugs (see ESDD procedures below).

If the subject discontinues HIV study drug dosing only, the following will occur:

- Be asked to return to the clinic within 72 hours of stopping HIV study drugs for the ESDD visit.
- HIV regimen may be changed, after discussion with the Medical Monitor. The new HIV regimen should be designed to allow continued dosing of LDV/SOF. LDV/SOF should be continued unless an HIV regimen cannot be constructed that would allow coadministration with the new HIV regimen.
- Remain in the study to complete the 12-week HCV treatment (see Section 6.4.1) and follow-up visits 4 and 12 weeks after the last dose of LDV/SOF, as described in Section 6.4.2.

If the subject discontinues both HIV and HCV study drug dosing, the following will occur:

- Be asked to return to the clinic within 72 hours of stopping study drugs for the ESDD visit.
- Remain in the study to return for follow-up visits 4 and 12 weeks after the last dose of LDV/SOF, as described in Section 6.4.2.

At the ESDD Visit, any evaluations showing abnormal results indicating that there is a possible or probable causal relationship with the study drugs, should be repeated weekly (or as often as deemed prudent by the Investigator) until the abnormality is resolved, returns to baseline, or is otherwise explained.

The following evaluations are to be completed at the ESDD Visit:

- Review of AEs and changes in concomitant medications

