8.5. Safety Analysis

All safety data collected on or after the date F/TAF-based ARV regimen was first dispensed up to the date of last dose of study drug(s) (either F/TAF-based regimen alone or in combination with LDV/SOF) plus 30 days will be summarized overall, according to the study drug(s) received.

Additionally, safety data collection on or after the first dose of LDV/SOF until the last dose of LDV/SOF plus 30 days (ie, during coadministration of HIV/HCV study drugs), will also be summarized.

Data for pretreatment and post-last-dose-plus-30-days will be included in data listings.

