8.5.2. Adverse Events

Clinical and laboratory adverse events (AEs) will be coded using the Medical Dictionary for Regulatory Activities (MedDRA). System Organ Class (SOC), High-Level Group Term (HLGT), High-Level Term (HLT), Preferred Term (PT), and Lower-Level Term (LLT) will be attached to the clinical database.

HIV treatment-emergent AEs are events that meet one of the following criteria up to 30 days after the permanent discontinuation of HIV study drug(s):

- AEs with onset dates on or after the first dose date of HIV study drug(s) and no later than 30 days after permanent discontinuation of HIV study drug(s), or,
- AEs that result in permanent study drug discontinuation of HIV study drug(s).

The number and percentage of subjects with treatment-emergent AEs (by SOC and PT) will be summarized as described in Section 8.5. A similar definition will be used to define HCV treatment-emergent AEs during coadministration of HIV/HCV study drugs. Additional summaries will include summaries for AEs by grade, Investigator's assessment of relationship to study drug, and effect on study drug dosing.

All treatment-emergent and non-treatment emergent AEs will be included in a data listing.

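### When HIV study drug stops before LDV/SOF, the SAP's Co-administration safety window closes earlier than the protocol's LDV/SOF window, and SAP 7.7 does not declare the change

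*SAP*

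**What the plan says.** **Protocol.** Section 8.5 asks for an additional summary of safety data collected "on or after the first dose of LDV/SOF until the last dose of LDV/SOF plus 30 days", and glosses that window as the time when HIV and HCV study drugs are given together. Section 8.5.2 defines HIV treatment-emergent AEs by a 30-day limit after HIV study drug is permanently discontinued, and adds: "A similar definition will be used to define HCV treatment-emergent AEs during coadministration of HIV/HCV study drugs". Section 8.5.3 asks for a matching summary of laboratory abnormalities.

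**SAP.** Section 7.1.1, Figure 7-1 note c, reads: "The co-administration period is terminated by permanent discontinuation of LDV/SOF or HIV study drug, which ever happens earlier". Table 7-1 gives the end date of Co-administration as "Minimum of HIV and HCV study drug last dose dates if applicable" and its safety cutoff as "30 days after Co-administration period end date". On outputs, the same section says: "Adverse events and laboratory abnormalities will be summarized for Part 1, Co-administration, and Whole Study periods respectively". By-visit laboratory results and vital signs use the Whole Study and Part 2 periods, and both of those run to the later of the two last doses. Section 7.7 states that nothing changes from the protocol's safety analysis.

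**The case in which the windows differ.** If only HIV study drug stops in Part 2, Protocol Section 6.5.1 has the subject "Remain in the study to complete the 12-week HCV treatment", provided a compatible new HIV regimen can be constructed. Protocol Section 6.9.1 says the same about LDV/SOF after virologic failure, and Figure 7-1 note d of the SAP describes the same course.

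**The concern.** One secondary objective is the safety and tolerability of 12 weeks of LDV/SOF in subjects who switched to an F/TAF-based regimen. The table that isolates that exposure is the Co-administration one. Its cutoff depends on whichever drug stops first, so it can close while a subject is still taking LDV/SOF. The subjects concerned have all stopped HIV study drug early, for reasons that include toxicity and virologic failure, so the shortening is not random with respect to safety. For AE counts it can only remove subjects from a row, never add them.

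The SAP also presents its windows as the protocol's. A reader of the report would take the Co-administration table to be the summary promised in Protocol Section 8.5.

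**Working it through.** The plan states no figure for this point, so there is none to reproduce. The check is date arithmetic.

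**Inputs**
- LDV/SOF course: 12 weeks = 84 days (Protocol Section 3.4).
- SAP cutoff: the earlier last dose + 30 days (SAP Table 7-1).
- Protocol cutoff: last LDV/SOF dose + 30 days (Protocol Section 8.5).
- d: the LDV/SOF day of the last HIV study drug dose. The documents do not give it, so it is varied. The full 84 days of LDV/SOF are assumed to be taken.

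**Formulas, for d ≤ 84**
- SAP cutoff = d + 30
- Protocol cutoff = 84 + 30 = 114
- Total days lost = 114 − (d + 30) = 84 − d
- Days lost while on LDV/SOF = max(0, 84 − (d + 30)) = max(0, 54 − d)

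| d | SAP cutoff | Protocol cutoff | Days lost | Of these, on LDV/SOF |
|---|---|---|---|---|
| 1 | 31 | 114 | 83 | 53 |
| 14 | 44 | 114 | 70 | 40 |
| 28 | 58 | 114 | 56 | 26 |
| 40 | 70 | 114 | 44 | 14 |
| 54 | 84 | 114 | 30 | 0 |
| 70 | 100 | 114 | 14 | 0 |
| 84 | 114 | 114 | 0 | 0 |

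At least two weeks of on-LDV/SOF data are lost only for stops on or before day 40. From day 54 on, only post-LDV/SOF follow-up is lost. A subject who keeps taking HIV study drug until LDV/SOF ends has the same cutoff under both documents.

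**AEs that stop LDV/SOF.** Under SAP Section 7.2.5.1 an AE is treatment-emergent if it meets either of two conditions. The first is onset between the period start and the cutoff. The second is a drug discontinuation dated no later than the period end. Once HIV study drug has stopped on day d, the period end is day d, so a later LDV/SOF discontinuation fails the second condition. The first still captures any AE with onset by day d + 30. An AE that begins during LDV/SOF treatment is therefore missing from the Co-administration row for LDV/SOF discontinuation only if its onset is more than 30 days after the HIV stop.

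**Where the data go instead.** AEs after the cutoff remain in the Whole Study tables, including the Whole Study row for AEs that stopped LDV/SOF, and in the listings (SAP Sections 7.1 and 7.2.6). By-visit laboratory results and vital signs remain in Part 2. Two gaps are left:
- Whole Study adds the 8 weeks before LDV/SOF and, for subjects who stay on HIV study drug, about 12 weeks after it. It therefore does not isolate the LDV/SOF window.
- Whole Study laboratory abnormalities are judged against Study Baseline, and Co-administration ones against Part 2 Baseline (SAP Section 7.3.2.1). An abnormality that is present on Day 1, clears by Week 8 and returns on LDV/SOF after the SAP cutoff, at no higher than its Day 1 grade, is treatment-emergent in neither table. The threshold-based liver summaries in Section 7.3.2.3 do not depend on baseline grade, so Whole Study still captures those values.

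**The case against.** The best defence is that the SAP follows the protocol's own description. Protocol Sections 8.5, 8.5.2 and 8.5.3 all call this the coadministration of HIV and HCV study drugs, and once HIV study drug stops there is none. The SAP groups subjects by the combination received (Section 3.2). Counting events that arise on LDV/SOF with a replacement HIV regimen would attribute a non-study combination to a study one. This makes a strict Co-administration table understandable and useful. It does not replace the explicit date rule in Protocol Section 8.5, and it does not explain why Section 7.7 declares no change.

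The second defence is that nothing is discarded and few subjects can be affected. This largely stands:
- Part 1 removes subjects who do not tolerate the switch or do not stay suppressed.
- Stops for resistance in Part 2 wait for a repeat test 2 to 4 weeks later and for resistance testing, which pushes them later.
- In the earlier single-arm LDV/SOF study in coinfected subjects (Protocol Section 1.3.2, on other HIV regimens), none of 335 had confirmed HIV rebound and none discontinued treatment for AEs.
- Each subject counts once per summary row, so a subject whose AE ended HIV study drug is probably already in the any-AE row.

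A reader might infer that everyone who stops HIV study drug in Part 2 loses weeks of on-LDV/SOF data. The SAP's own 30 days rule that out for stops from day 54. A reader might also infer that any AE ending LDV/SOF after the HIV stop disappears from the discontinuation row. The either-condition rule limits that to late onsets.

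**Conclusion.** The conflict is real and undeclared. Protocol Section 8.5 and SAP Table 7-1 set different end dates for the same summary, and Section 7.7 is wrong to say that nothing changes. For a subject who stops HIV study drug on LDV/SOF day d and completes 84 days of LDV/SOF, the Co-administration AE and laboratory-abnormality tables lose 84 − d days, max(0, 54 − d) of them on drug. The most that can be lost on drug is 53 days.

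The documents do not support a claim that LDV/SOF event rates will be materially understated. They give neither the number of subjects who stop HIV study drug first nor the timing, and the number affected may be zero or very few. The point rests on the definition: as planned, no AE or laboratory-abnormality table covers the protocol's LDV/SOF window. It is worth correcting because it is cheap, not because a large effect is expected.

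**What to change.** Run the AE and laboratory-abnormality summaries on the protocol window, from first LDV/SOF dose to last LDV/SOF dose + 30 days, and use the last LDV/SOF dose as the period end date in Section 7.2.5.1. Either route works:

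1. Change the Co-administration row of Table 7-1 and Figure 7-1 note c.
2. Keep the strict Co-administration period and add an on-LDV/SOF summary beside it. In that case, correct Section 7.7 to declare the strict period as a departure from Protocol Section 8.5.

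Under either route, flag events that start after HIV study drug was stopped.

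The cost is one table row and a footnote, or one extra set of summaries. No new data are needed. The downside is that a few events may arise on LDV/SOF with a replacement HIV regimen. The flag identifies them.
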